11.5 Other Safety Measures

11.5.1 Vital Signs and Body Weight

Vital signs will be assessed on various visits and timepoints thought the study. Vital signs and body weight results collected during the on-treatment period will be presented by cohort/arm for the SAF. Data collected during the pre-treatment and post-treatment periods will only be listed.

The following will be assessed:

1. Pulse rate (beats/min),
2. Respiratory Rate (breaths/min),
3. Systolic and diastolic blood pressure (mmHg),

Statistical Analysis Plan

SMS-0571/CyPep-1

V3.0 Final

04-Jun-2024

4. Body temperature (°C).

Observed values and changes from baseline for vital signs and body weight will be summarized at each visit and timepoint, as applicable; maximum and minimum most extreme change will be summarized as well.

Additionally, body weight, pulse rate, body temperature, systolic blood pressure, and diastolic blood pressure will be summarized based on markedly abnormal criteria defined in [Table 5](#) below.

Table 5. Markedly Abnormal Criteria for Vital Signs

Vital Sign	Markedly Abnormal Criteria
Pulse rate (beats/min)	< 60 beats/min > 100 beats/min
Body temperature (°C)	≤ 35 °C ≥ 38 °C
Systolic blood pressure (mmHg)	120-139 mmHg, inclusive (CTCAE grade 1) 140-159 mmHg, inclusive (CTCAE grade 2) ≥ 160 mmHg (CTCAE Grade 3)
Diastolic blood pressure (mmHg)	80-89 mmHg, inclusive (CTCAE grade 1) 90-99 mmHg, inclusive (CTCAE grade 2) ≥ 100 mmHg (CTCAE grade 3)
Body weight (kg)	5 to <10% decrease from baseline 10 to <20% decrease from baseline ≥ 20% decrease from baseline

Incidence of markedly abnormal values will be presented overall (including unscheduled visits) and at each scheduled visit. For pulse rate and temperature, both high and low values will be presented separately such that subjects can be counted in both categories, if applicable.

Mean (\pm SD) vital signs and body weight data will also be plotted over time per cohort/arm for SAF. For vital signs, an additional figure presenting each cycle on different page, including 2 x 2 (or 2 x 3, as applicable) matrix of figures of treatment days in each cycle will be created for SAF. The second figure allows for detailed inspection of data collected in a short timeframe before and after dosing; the first figure will provide general visual trend over entire study duration.

All vital signs and body weight data will be presented in subject data listings for all subjects. Markedly abnormal vital sign values will be flagged as such in the listing.

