7. Medical history should include details of cancer onset, prior surgery and past cancer treatments.
8. **For Arms A, B and C:** Arrangements to be made for any tumor material to be sent for analysis are described in the laboratory manual. Tumor biopsies (should be available from at least one injected lesion at screening and at Week 6 of Cycle 1) will be taken from injected and, whenever available, non-injected lesions at screening. At Week 6 (± 1 day), the same lesion(s) has to be used for the biopsy sampling. No biopsy is to be taken if tumor is inaccessible, biopsy not in subject's best interest or thought to be dangerous or if subject declines to consent to biopsy. **For Arm D:** Tumor biopsy from at least one injected lesion at screening and at Week 6 is highly desired but not mandatory.
9. ECOG performance status assessment, height, weight, and physical examination may be done the day before CyPep-1 administration or pembrolizumab administration (if pembrolizumab administration day is different from CyPep-1 scheduled day) before dosing for logistical reasons.
10. For vital signs (blood pressure, pulse and temperature), a time window of ± 5 min is allowed. **For Arms A, B and C:** Vital signs before and 15 min, 30 min, 1 h, 2 h and 4 h after treatment will be recorded for all subjects during Cycle 1 on Days 1, 15, 29 and 36 (DL/T/LT period). For all subsequent cycles, vital signs will be recorded on Day 1 before and 15 min, 30 min, 1 h, 2 h and 4 h after treatment. For all other Days of each cycle, only before treatment and if abnormal to be followed up at the investigator's discretion. **For Arm D:** Vital signs before and 15 min, 30 min, 1 h, 2 h and 4 h after treatment will be recorded for all subjects on each dosing day. For subjects who have no clinically significant abnormality with vital signs reported during the first four doses of CyPep-1 (on V1 (D1), V2 (D8), V3 (D15) and V4 (D22)), vital signs will be recorded before and 15 min, 30 min, and 1 h after treatment on all the subsequent dosing days.

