8.2 Baseline definition

Baseline value for all assessments will be defined as the last non-missing value recorded prior to the treatment start date(time) (as defined in Section [8.3](#) below).

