8.3 Reference Dates

The following reference dates are defined:

1. **Screening date** is defined as the eCRF provided date on which a subject was screened for trial entry. If screening procedures took several days, the first of these days is considered as screening date.
2. **Informed consent date** is defined as the date of Informed Consent signed by the subject collected on Informed Consent eCRF page.
3. **Treatment start date(time)** is defined as the date(time) of first dose of any study drug (Cy-Pep1 or pembrolizumab). **CyPep-1 treatment start date(time)** is defined as the date(time) of first dose of CyPep-1. **Pembrolizumab treatment start date(time)** is defined as the date(time) of first infusion of pembrolizumab.
4. **Treatment end date(time)** is defined as the date(time) of last dose of any study drug (Cy-Pep1 or pembrolizumab). **CyPep-1 treatment end date(time)** is defined as the date(time) of last dose of CyPep-1. **Pembrolizumab treatment end date(time)** is defined as the end date(time) of last infusion of pembrolizumab.
5. **End of study date** is defined as Date of study completion/discontinuation recorded on the End of Study Form in the eCRF.

Statistical Analysis Plan

SMS-0571/CyPep-1

V3.0 Final

04-Jun-2024

6. Age will not be calculated and will come directly from the eCRF. The eCRF uses the demographics assessment date at Screening as its reference date for age calculation.
7. Safety data, such as AEs and laboratory assessments, will use the treatment start date as a reference date.
8. Efficacy data will use the treatment start date as a reference date.
9. **Study day** will be based on treatment start date as a reference date.

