8.6 Baseline and Post-Baseline Changes

Unless stated otherwise, baseline and post-baseline change values will be based on the [Table 2](#) below.

Table 2. Baseline and Post-Baseline Changes

Variable	Definition
Baseline value	Baseline definition is provided in Section 8.2 .
Post-baseline value	Values collected after the treatment start date(time).

Statistical Analysis Plan

SMS-0571/CyPep-1
V3.0 Final
04-Jun-2024

Variable	Definition
Change from baseline	Post-baseline value – baseline value.
Percentage change from baseline	$(Post\text{-}baseline\ value - baseline\ value) / baseline\ value \times 100$. If baseline value is equal to 0, percent change from baseline will be missing.
Most extreme change	The maximum most extreme change will be based on the maximum post-baseline value. The minimum most extreme change will be based on the smallest post-baseline value. This calculation will consider all assessments collected during the on-treatment period, scheduled or unscheduled
Maximum reduction from baseline	The maximum reduction from baseline will be based on the minimum post-baseline value collected and calculated per the change from baseline formula above. Maximum reduction from baseline will only be calculated for tumor measurements. Post-baseline values will be considered until an overall response of iCPD or start of new anticancer treatment.
Maximum percentage reduction from baseline	The maximum percentage reduction will be the percentage change from baseline for the maximum reduction from baseline.

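### No planned table gives each subject's change in vital signs from the same-day pre-dose reading: after Day 1, every tabulated change refers back to one pre-treatment baseline

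*SAP*

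**What the plan says.** The analysis rule comes from three parts of the SAP.

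- SAP 8.2 sets the reference: "Baseline value for all assessments will be defined as the last non-missing value recorded prior to the treatment start date(time"). SAP 8.3 adds that treatment start "is defined as the date(time) of first dose of any study drug (Cy-Pep1 or pembrolizumab"), so in Arm B the infusion can be the event that fixes it.
- SAP 8.6, Table 2, calls post-baseline everything that meets "Values collected after the treatment start date(time") and defines change as "Post-baseline value – baseline value". For the most extreme change it says: "This calculation will consider all assessments collected during the on-treatment period, scheduled or unscheduled". No change from a same-day pre-dose value is defined.
- SAP 11.5.1 applies this to vital signs: "Observed values and changes from baseline for vital signs and body weight will be summarized at each visit and timepoint, as applicable".

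The data collection is richer than that rule. Footnote 10 of the protocol's Schedule of Assessments says, for Cycle 1 in Arms A to C: "Vital signs before and 15 min, 30 min, 1 h, 2 h and 4 h after treatment will be recorded for all subjects". For later cycles it continues: "For all subsequent cycles, vital signs will be recorded on Day 1 before and 15 min, 30 min", with the remaining timepoints up to 4 hours. On the other days of later cycles only a pre-dose reading is required.

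SAP 11.5.1 also plans a second vital-signs figure, with panels for the treatment days of each cycle, meant for looking at readings close to dosing. It also lists every reading by subject.

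**The concern.** Serial readings over 4 hours are taken to detect acute effects. Protocol 5.6.1 requires observation over that time for immediate reactions to the injection, Protocol 1.9.1 names low blood pressure among the possible signs of an allergic reaction, and Appendix E stages anaphylactic reactions partly by changes in blood pressure and pulse. The natural measure of such an effect is the subject's post-dose value minus the same day's pre-dose value.

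The planned change answers a different question. A 30-minute reading on Day 29 is compared with a value from about 28 days earlier. On Cycle 4 Day 1 (Day 127 in SAP Appendix 4) the gap is about 126 days. Disease course, new medication and ordinary day-to-day variation all enter the difference. The most extreme change has the same reference, so it can miss an acute fall in one subject and report slow drift as an extreme in another.

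**Working it through.** The documents give no power, precision or variance figure for vital signs, so there is no planned figure to reproduce. The check has three steps.

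**1. What can be recovered from the planned tables.** Write B for the fixed baseline, P for the same-day pre-dose reading and Y for a post-dose reading.

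- Group mean: mean(Y − B) − mean(P − B) = mean(Y − P), if the same subjects contribute to both. From the second dosing visit on, P falls in the on-treatment period (SAP 8.5) and is therefore tabulated. The group-mean acute change can be obtained by subtraction.
- SD: Var(Y − P) = Var(Y − B) + Var(P − B) − 2 Cov(Y − B, P − B). No planned table gives the covariance, so the SD of the same-day change cannot be obtained.
- Extremes: the minimum of Y − B need not occur in the same subject, or at the same time, as the minimum of Y − P. They cannot be obtained either.

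**2. How far the two measures can differ in one subject** (assumed systolic values in mmHg, not from the documents).

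- B = 120, P on Day 29 = 145, Y at 30 minutes = 118. Planned change: 118 − 120 = −2. Same-day change: 118 − 145 = −27.
- B = 120, P = Y = 100 some months later. Planned change: 100 − 120 = −20. Same-day change: 0.

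SAP Table 5 would not separate these cases. Its systolic and diastolic criteria are all for high values. It has low criteria for pulse and temperature, but these are absolute and do not refer to the pre-dose reading.

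**3. Illustrative precision.** Assume reading = subject + visit effect (SD s_b) + reading error (SD s_w), with the same acute effect in every subject.

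- SD(Y − B) = √(2s_b² + 2s_w²) and SD(Y − P) = √(2s_w²).
- The ratio is √(1 + (s_b/s_w)²). For s_b/s_w = 0.5, 1.0, 1.5 and 2.0 it is 1.12, 1.41, 1.80 and 2.24.
- In terms of correlations, SD(Y − P)/SD(Y − B) = √((1 − r_within)/(1 − r_between)). With assumed r_within = 0.8, r_between = 0.4 gives √(0.2/0.6) = 0.58, and r_between = 0.7 gives √(0.2/0.3) = 0.82. The variance ratios are 3.0 and 1.5.
- With s_w = 6 mmHg, an acute change of −10 and mean drift of +5 (all assumed), the mean change from the fixed baseline is 5 − 10 = −5. Its SD is √(2(9 + 36)) = 9.5 for s_b = 3 and √(2(144 + 36)) = 19.0 for s_b = 12. The same-day change has mean −10 and SD √72 = 8.5.

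If the acute effect varies between subjects, that variance adds to both measures and the ratio moves towards 1.

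**The case against.** The strongest reply is that the plan already shows readings before and after dosing. Observed values are tabulated at each visit and timepoint, the second figure is designed for this inspection, and all readings are listed with markedly abnormal values flagged. In arms this small, a reader can work through a listing. This stands at group level, and it rules out the reading that acute effects are hidden or that the plan offers no view around dosing. Nor can one say that the second figure shows only arm means: SAP 11.5.1 states mean and SD for the first plot, does not spell out the content of the second, and leaves layouts to separate shells. The reply does not supply a tabulated within-subject change, and a reaction in one subject can disappear in an arm mean.

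A second reply is that acute reactions are captured as adverse events, which are the main primary endpoint, and that no test or decision rule uses vital-sign change. This is correct and limits the stakes. Vital signs enter the primary endpoint only among the additional safety parameters.

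A third is that a same-day reference is not clean either. In Arm B, CyPep-1 follows pembrolizumab by 30 to 60 minutes on shared days (Protocol 5.3.2), and after Cycle 1 the serial readings fall on Day 1, normally the infusion day. A pre-infusion reference would mix infusion and injection effects. Premedication, where given, may also fall between the two readings, and footnote 10 sets no maximum interval from the pre-dose reading to the injection. This stands and must be handled in the fix.

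A reader might also infer that the planned analysis wastes the equivalent of 1.5 to 3 times the subjects. The documents do not support that: the correlations are assumed, and the summary is descriptive with no precision target.

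**Conclusion.** The point holds as a missing summary. After Day 1, the tabulated change in post-injection vital signs and the most extreme change rest on the fixed pre-treatment baseline. No planned table gives the within-subject same-day change, its SD or its extremes. This follows from the SAP's definitions and needs no assumption.

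The scope is limited. On Day 1 the baseline is normally the same-day pre-dose value, except that in Arm B it precedes the infusion. The days affected are the later Cycle 1 dosing days, including weekly visits where used, and Day 1 of later cycles. Arm D stopped after one subject (SAP 6.1, footnote 1).

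The size cannot be set from the documents. The SD ratios of 1.12 to 2.24 depend wholly on assumed variance components. Only the direction is general under that model: any visit-to-visit variance makes the planned change noisier than the same-day change. The gap does not invalidate the safety analysis or affect any planned decision, but it is worth closing because the data are collected and the cost is small.

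**What to change.** In SAP 11.5.1, alongside the existing summaries:

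- For every post-dose timepoint, add the change from the same-day pre-dose value (n, mean, SD, median, minimum, maximum).
- Add each subject's largest same-day rise and largest same-day fall per dosing day. This would show an acute pressure fall without needing a new threshold in Table 5.
- For Arm B days with both drugs, state which reading is the reference: the one before the infusion, or one between infusion and CyPep-1 injection if recorded. If it is the pre-infusion reading, footnote that the change mixes infusion and injection effects.
- Keep change from the pre-treatment baseline for pre-dose values, body weight and long-term trend.

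This fits the SAP's structure. Table 2 in 8.6 allows departures where a section states them, and Appendix 5 already uses a just-before-injection baseline for injected target lesions. Any statement about gain in precision should be labelled illustrative. The cost is one derived reference value and one table, with no new data and no change to trial conduct.

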11.5.2 ECG

ECG will be assessed as specified in the protocol Schedule of Assessments. The following ECG parameters will be collected: PR interval (msec), QRS interval (msec), QT interval (msec), QT interval corrected for heart rate using Fridericia's formula (QTcF) (msec), and Heart Rate (beats/min). ECG parameters will come directly from the eCRF and will not be calculated during analysis (calculation rules for QTcF are documented in the *Study Design Specification* document). ECG results collected during the on-treatment period will be presented by cohort/arm for the SAF. Data collected during the pre-treatment and post-treatment periods will only be listed.

Observed values and changes from baseline for ECG parameters will be summarized at each visit; maximum and minimum most extreme change will be summarized as well.

Shift from baseline to worst post-baseline interpretation (normal; abnormal, not clinically significant; abnormal, clinically significant) will be summarized.

All ECG data will be presented in a by subject data listing for all subjects.

11.5.3 Physical Examinations

Physical examination results will only be presented in subject data listings for all subjects.

11.5.4 ECOG Performance Status

ECOG data will be summarized using score categories 0-5 at scheduled visits during the on-treatment period and with shift from baseline score to the worst post-baseline score by cohort/arm for the SAF. Best to worst ECOG value is defined in the order: Missing, Grade 0, Grade 1, Grade 2, Grade 3, Grade 4, Grade 5. In case a subject dies while on treatment (i.e., primary reason for treatment discontinuation is death), this subject is counted as

Statistical Analysis Plan

SMS-0571/CyPep-1
V3.0 Final
04-Jun-2024

having a shift from baseline value to death, even if ECOG score of 5 is not recorded in the eCRF. Data collected during the pre-treatment and post-treatment periods will only be listed.

ECOG data will be presented in subject data listings for all subjects. Worst post-baseline scores will be flagged in the listing.

Statistical Analysis Plan

SMS-0571/CyPep-1

V3.0 Final

04-Jun-2024

13 APPENDIX

13.1 APPENDIX 1. PARTIAL DATE CONVENTIONS

ALGORITHM FOR TREATMENT EMERGENCE OF ADVERSE EVENTS:

For AEs with missing or partial start and end dates, the following imputation rules will be applied (i.e., “worst case” scenario):

AE start datetime:

Impute to *treatment start datetime* if:

- *AE start time* unknown and *AE start date* = *treatment start date*.
- *AE start day* is missing from *AE start date* and *AE start month* = *treatment start month*.
- *AE start month* is missing from *AE start date* and *AE start year* = *treatment start year*.
- *AE start datetime* fully missing.

Else impute *AE start datetime* as earliest possible datetime (i.e., 00:00 if time unknown, first day of month at 00.00 if time and day unknown or 1st of January at 00.00 if time, day and month are unknown).

AE end date:

If *AE end day* and/or *AE end month* is missing, *AE end day* and /or *AE end month* is imputed with the last day of the month and/or last month of the year. If the imputed *AE end date* falls after *end of study date*, the *AE end date* is imputed with the *end of study date*.

Fully missing AE end dates won't be imputed, unless end date is missing and AE is marked as not resolved at time of death – in that case, AE end date will be imputed as date of death.

Imputed AE start and end dates will only be used for analysis purposes (e.g., generating summary tables or figures). In the listings, the incomplete study dates will be presented as collected (i.e., as incomplete).

An algorithm for determining treatment emergence of an AE is given in [Table 6](#) below.

Table 6. Algorithm for Treatment Emergence of Adverse Events

Start date	Rule
Known	If AE start datetime < treatment start datetime , not TEAE. If AE start datetime ≥ treatment start datetime , then TEAE.
Partial/Missing	If imputed AE datetime < treatment start datetime , not TEAE. If imputed AE datetime ≥ treatment start datetime , then TEAE.

ALGORITHM FOR MEDICATIONS AND PROCEDURES PRIOR / CONCOMITANT / SUBSEQUENT TO STUDY TREATMENT:

Partial start datetime

Impute to *treatment start datetime* if:

- *Start time* unknown and *start date*=*treatment start date*.
- *Day* is missing from *start date* and *start month*=*treatment start month*.
- *Month* is missing from *start date* and *start year*=*treatment start year*.

Else impute *start datetime* as earliest possible datetime (i.e., 00:00 if time unknown, first day of month at 00.00 if time and day unknown or 1st of January at 00.00 if time, day and month are unknown).

For procedures, only impute start date (time is not collected for procedures).

Partial stop datetime

Impute *stop datetime* as latest possible datetime (i.e., 23:59 if time unknown, last day of month at 23.59 if day unknown or 31st December at 23.59 if day and month are unknown). If the imputed *stop datetime* falls after *end of study date*, the *stop datetime* is imputed with the *end of study date* at 23:59.

For procedures, only impute end date (time is not collected for procedures).

An algorithm for classifying medications and procedures is given in [Table 7](#) below.

Statistical Analysis Plan

SMS-0571/CyPep-1
V3.0 Final
04-Jun-2024

Table 7. Algorithm for Medications and Procedures Prior / Concomitant / Subsequent to Study Treatment

Stop date	Rule*
Known	If stop date(time) < treatment start date(time) , assign as prior. If treatment start date(time) <= stop date(time) <= treatment end date(time) , assign as concomitant. If treatment end date(time) < (imputed) start date(time) , assign as subsequent.
Partial	If imputed stop date(time) < treatment start date(time) , assign as prior. If treatment start date(time) <= imputed stop date(time) <= treatment end date(time) , assign as concomitant. If treatment end date(time) < (imputed) start date(time) , assign as subsequent.
Missing	If treatment end date(time) < (imputed) start date(time) , assign as subsequent. Else, assign as concomitant.

*For medications use datetime, for procedures use date.

Statistical Analysis Plan

SMS-0571/CyPep-1
V3.0 Final
04-Jun-2024

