6.1 General Study Design

This is a combined Phase I/IIa, open-label, dose escalation followed by dose expansion trial in subjects with advanced solid cancers. The trial consists of two phases and multiple arms, as shown in the diagram below ([Figure 1](#)).

Figure 1. Schematic trial design of Phase I (dose escalation, N=12) and Phase IIa (dose expansion Arm A, N=9 up to 18; combination Arm B, N=15; dose expansion liver metastases Arm C, N=9; and dose expansion melanoma Arm D, N=30)¹

For both phases and all trial arms, subjects will stay in the trial until end of trial or until confirmed disease progression, unacceptable toxicity, death or discontinuation for any other reason.

Phase I – dose escalation:

In this phase of the trial, safety and tolerability will be documented and the MTD/RP2D will be determined. Cohorts of 3 subjects will receive IT injections with CyPep-1. The DLT observation period for each dose level will be 6 weeks (5 weeks of trial treatment and 1 week of safety follow-up).

Screening will occur during the 4 weeks prior to start of CyPep-1 treatment.

In three dose cohorts of 3 subjects each, subjects will receive CyPep-1 IT at different concentrations (dose escalation) and volumes (depending on tumor size), i.e., 0.5 mg/mL, 2 mg/mL, or 5 mg/mL, respectively. These dose concentrations have been selected based on previous pre-clinical experience with CyPep-1.

Each subject will receive IT injection(s) with CyPep-1 on Day 1 of Weeks 1, 3, and 5, respectively. After each CyPep-1 administration, subjects will be required to stay at the clinic for at least 4 hours for safety and, for those in which PK will be assessed, also for PK monitoring. The data from the additional three subjects in cohort 3 will be used for further confirmation of RP2D. The following CyPep-1 administrations are planned as continuous Q2W administrations.

For each dose cohort, at least 24 hours must elapse between each subject to start treatment with CyPep-1. No intra-subject dose escalation is allowed.

¹ Note: as per sponsor confirmation letter from 14Apr2023, recruitment in Arm D was stopped after recruiting one subject due to recruitment difficulties. This SAP presents information regarding Arm D as presented in protocol v10.0/v10.1 (pre-dating the information letter).

Statistical Analysis Plan

SMS-0571/CyPep-1

V3.0 Final

04-Jun-2024

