11.1 Adverse Events

An adverse event (AE) is defined as any untoward medical occurrence in a clinical trial subject administered with a medicinal product and which does not necessarily have a causal relationship with this treatment.

Subjects will be monitored for AEs from the time of Informed Consent Form (ICF) signature until the FU visit (or until EoT, if it occurs more than 30 days after the last CyPep-1 administration for Phase I and Arms A and C and D; for Arm B refer to Clinical Study Protocol Section 7.2.1.3). After the FU visit (or EoT visit, if it occurs more than 30 days after the last CyPep-1 administration), only ongoing AEs or serious adverse events (SAEs) related to CyPep-1 administration will be collected.

A serious AE is any untoward medical occurrence or effect that at any dose:

- Results in death (not due to disease progression),
- Is life-threatening (the subject was at risk of death at the time of the event; it does not refer to an event that hypothetically might have caused death if it were more severe),
- Requires hospitalization or prolongation of existing hospitalization,
- Results in persistent or significant disability or incapacity,
- Is a congenital anomaly or birth defect.

The following are not considered (and do not need to be reported) as SAEs:

- Hospitalization due to a social indication,
- Elective pre-planned hospitalizations for treatment of an existing condition prior to entering the trial,
- Hospitalizations due to tumor-related symptoms or tumor progression.

Any event that does not meet the above criteria may also be considered by the investigator to be an SAE, based on appropriate medical and scientific judgment.

All AEs reported after the start of first dose of study treatment (CyPep-1 or pembrolizumab) are considered treatment-emergent.

AEs will be assessed using CTCAE v5.0, including start and stop dates, severity, relationship to CyPep-1, outcome and action taken. Section 7 of the Clinical Study Protocol provides detailed instructions on AE reporting and definitions related to it.

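### The AE start-date imputation does not check the end date, so an event recorded as over before the first dose can be counted as treatment-emergent

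*SAP*

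**What the plan says.** SAP Appendix 1 introduces its rules for incomplete AE dates with "the following imputation rules will be applied (i.e., “worst case” scenario". An incomplete start becomes the treatment start datetime if the day is missing and the month matches that of first dose, if the month is missing and the year matches, or if nothing is recorded. Another rule covers a missing clock time on the day of first dose and is not at issue here. All other incomplete starts go to the earliest possible datetime.

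For a partial or missing start, Table 6 compares the imputed value with treatment start: "If imputed AE datetime ≥ treatment start datetime , then TEAE". The end-date paragraph fills in end dates only; it does not feed back into the start or the flag. SAP 8.7 and 11.1.2 refer to Appendix 1 and add no check.

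Events before dosing are within the data collected. SAP 11.1 states "Subjects will be monitored for AEs from the time of Informed Consent Form (ICF) signature until the FU visit", and SAP 6.1 states "Screening will occur during the 4 weeks prior to start of CyPep-1 treatment". SAP 11.1 ties treatment emergence to the period after the start of first dose. Protocol 8.1.3 and the last item of the by-SOC-and-PT list in SAP 11.1.3 call for pre-treatment AEs to be summarised separately.

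**The concern.** Assuming the worst is reasonable when the timing of an event is unknown. Here it is known: if the recorded end is before the first dose, the event cannot have started at or after it, however little of the start date was captured. The rule replaces that knowledge with a start later than the recorded end.

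What is at stake is the content of the TEAE tables, which are the main tabular summary of safety and are shown by cohort or arm. Some columns are very small: Cohorts 1 and 2 were planned at three subjects each, and a footnote in SAP 6.1 says that Arm D stopped after one. A screening event filed under the wrong heading would be visible there and would be missing from the pre-treatment table where it belongs.

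**Working it through.** The plan states no figure to reproduce, so the check applies the rules as written to test records and compares them with the neighbouring rules.

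**Inputs.** The start rules and Table 6 (SAP Appendix 1); duration = stop − start + 1 day (SAP 11.1.2); a pre-dose window of up to 4 weeks (SAP 6.1). Assumed for illustration: first dose 20 March 2022 at 10:00, AE end date 10 March 2022.

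| Recorded start | Imputed start | Table 6 as written | With an end-date check |
|---|---|---|---|
| March 2022, day missing | 20 March, 10:00 | TEAE | not TEAE |
| 2022, day and month missing | 20 March, 10:00 | TEAE | not TEAE |
| fully missing | 20 March, 10:00 | TEAE | not TEAE |
| February 2022, day missing | 1 February | not TEAE | not TEAE |
| 5 March 2022, complete | none needed | not TEAE | not TEAE |

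The first three rows are wrong as written. The last two are controls and are right either way. In the first three rows the duration formula gives 10 − 20 + 1 = −9 days. An event ending on 19 March would give 19 − 20 + 1 = 0.

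**Comparison with Table 7.** Medications and procedures use the same imputation for partial starts, but Table 7 tests the stop date first, and a stop before treatment start makes the record prior. A drug given for the event in the first row, with the same partial start and a stop on 10 March, would be prior, while the event it treated would be treatment-emergent.

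**How often the start conditions could be met.** Assume dosing dates spread evenly over a 365-day year, a full 28-day screening period and onset equally likely on each pre-dose day. There are 365 × 28 = 10,220 pre-dose days.

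- Same calendar month as first dose: the sum of min(day of month − 1, 28) is 462 for a 31-day month, 434 for a 30-day month and 378 for February. The total is 7 × 462 + 4 × 434 + 378 = 5,348, and 5,348 / 10,220 = 52%.
- Same calendar year: the days falling in the previous year number 28 + 27 + … + 1 = 406, and (10,220 − 406) / 10,220 = 96%.

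So, among screening events with an incomplete start, the trigger is not rare: about half if the day is missing, nearly all if the month is missing, and all if the whole date is missing. These shares say nothing about how many such records exist.

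**Size in a table.** One misclassified subject in a preferred-term row is 1/3 = 33 percentage points in a cohort of 3, 1/9 = 11 in Arm A as planned, and 1/15 = 7 in Arm B. The any-TEAE row moves only if that subject has no other TEAE.

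**The case against.** The strongest reply is that the rules are declared worst-case and the error runs in the cautious direction: TEAEs can be over-counted, never under-counted. That stands. A reader might infer that the rule is anti-conservative or understates toxicity, and the documents do not support this.

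A reader might also infer that the primary endpoint or the dose decisions are compromised. The text does not bear that out. The primary endpoint covers type and number of AEs together with DLTs, MTD and TLTs. A misclassified event remains in the comprehensive AE listing and only moves between two summaries. DLTs and TLTs need an investigator's judgement of at least possible relatedness, which an event over before dosing should not receive, and SAP 7.3 places the Dose Escalation Committee's analyses outside the SAP. Tables of related or Grade 3 and higher TEAEs could pick up such an event through the missing-data rules, but only if relatedness or severity were missing too.

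Nor do impossible durations reach any summary. SAP 11.1.2 confines AE duration and study day to listings, SAP 8.4 shows relative days there only from non-imputed dates, and Appendix 1 prints incomplete dates as collected. SAP 11.1.2 does allow duration to be computed from an imputed start, so at most an odd value could appear in a listing.

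Finally, Protocol 7.2.2 makes the dates of occurrence and resolution required items and treats conditions present at screening as medical history. Protocol 9.1 provides for validation and queries, and a data review meeting precedes lock. These controls make surviving cases few. They do not repair a rule that gives the wrong answer for any case that remains.

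**Conclusion.** The rule is wrong as written for a narrow class of records: AEs arising after consent, with an incomplete start meeting one of the three conditions and an end date known, or at the latest possible, to fall before the first dose. For these, Table 6 gives a classification that contradicts SAP 11.1 and removes the event from the pre-treatment table. The consequence is an over-count in the TEAE summary tables. That the number is small is an expectation based on the data controls, not a figure in the documents. This is a low-priority correction, worth making because it costs almost nothing and because single subjects are visible in the smallest columns.

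**What to change.** Add a first step to Table 6: if the AE end date, as recorded or at its latest possible value when partial, is before the treatment start date, the AE is not treatment-emergent and its start is not imputed to treatment start; otherwise the existing worst-case rules apply.

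Setting the flag is enough, since the pre-treatment table needs no start date. If a start is wanted, it should be imputed no earlier than the informed consent date. Using the earliest date compatible with the recorded part would be undefined for a fully missing start. For a year-only start it would give 1 January, which in the example is before 20 February, the earliest day of the 28-day screening period.

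Uncertain cases stay as they are. With first dose on 20 March, an end recorded only as March has a latest possible value of 31 March and remains a TEAE.

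The cost is one SAP sentence and one condition in the derivation program, with no new data. Listing the affected records at the data review meeting would also show how many there are.
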